Cluster randomized controlled trial: We will select up to 18 (2 pilot + 16 for full implementation) schools from the Urban District of Lusaka to receive the SKILLZ-Girl curriculum. Of the total (up to 18), half will be randomly allocated to host the standard SKILLZ-Girl curriculum, and the remaining half (e.g., up to eight) will be randomized to either enhanced SKILLZ-Club. Those schools randomized to standard SKILLZ Girl curriculum will only have access to SOC clubs. Those schools selected for enhanced SKILLZ Girl curriculum will offer SKILLZ Club. See **Figure 3** for study allocation flow.

Figure 3. School Selection Flow Chart

[figure not shown]
ONGOING REFERRAL TO COMMUNITY CARE FOR SERVICES

We anticipate that most of our evaluation cohort will not be HIV-infected. Thus, the retention to SRH analysis drives the sample size calculation of 351 girls using contraception at the end of two years, with, and risk ratio difference of 0.3 (30%) between the SOC and enhanced SKILLZ-Club schools. To realize the 351 needed to meet requirements for estimate sensitivity, we augment the initial sample size receiving the SKILLZ-Girl curriculum accounting conservatively for 25% uptake of SRH methods and multiplying by two to assess the difference within each SKILLZ-Girl model (phase 1) and accounting for attrition across the two years of follow-up (12.5%) resulting in a starting sample size of 3159 $((351/0.25) \times 2) \times 1.025$. **SKILLZ-CLUBS** will act as an extension to the SKILLZ-Girl curriculum enabling participants to seamlessly transition from the SKILLZ-Girl curriculum into the SKILLZ-Club. We anticipate minimal attrition (~15-20%). Participants will spend the majority of the study window in SKILLZ-Club and it is through the SKILLZ-Club affiliation that we will follow-up and ascertain outcomes for those enrolled longitudinally.

For the small minority of girls found to be HIV-infected across all schools where the study will be conducted, we will evaluate linkage to care and on treatment, VLS, and retention in care for a period of two years. These girls will be encouraged to continue on to the HIV positive-specific SKILLZ-Plus facility-based curriculum. We will quantitatively measure the impact of SKILLZ-Plus on linkage to care and treatment, retention and viral load at 6, 12, and 24 months after diagnosis (or since participant is identified by GRS as HIV+) using SmartCare data and compare to an existing matched cohort.

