SmartCare electronic data: All antiretroviral therapy services offered as part of the study will be captured in SmartCare, which permits measuring of utilization and clinical outcomes (i.e., Linkage to Care, VLS) at soccer events, mobile clinics, and public clinics in Lusaka. VLS is defined as below detection, i.e. less than 50 copies/ml. Retention in care will also be measured using SmartCare data on pharmacy visits and defined as accessing pharmacy within a 90-day window of visits. Consent will be requested from all participants as part of the consent process to access their SmartCare records.

Youth-Friendly services electronic data: Depending on the location of the school, the girl's residential address and/or her own personal preferences, participants will be referred to either the PEPFAR Funded DREAMS houses or the M.A.C. funded youth-friendly spaces based in local MOH clinics in order to access ongoing SRH services after the events (this will include accessing PrEP, STI testing and contraceptive methods). All interactions with the DREAMS houses or M.A.C centres (including meeting with counselors, referral and uptake of services) are captured in their respective electronic databases. Consent will be requested from all participants as part of the consent process to allow researchers to access either DREAMS or M.A.C data should they chose to access either of these services.

Survey at baseline: A baseline survey will be administered to all to collect information on school characteristics, sexual behavior, age, HIV knowledge, maternal education, baseline HIV status, and sexual/reproductive health uptake and retention. These variables will be used as covariates and moderators for service uptake and retention. The target sample of 3,200 girls will respond to a survey self-administered using REDCap software upon informed consent. The survey will be available in English, Nyanja and Bemba. Coaches and study staff will on site be help girls navigate the survey.

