Survey post-SKILLZ-Girl event, 3-, 12-, and 24 months: All girls (regardless of HIV status) will respond to a REDCap survey to collect information on sexual behavior, HIV knowledge, maternal education, sexual/reproductive health uptake and retention. Post-SKILLZ-Girl survey data will be used to assess the effect of SKILLS Girl and SKILLZ-Club on the outcomes of interest. In schools selected to offer SKILLZ-Club, surveys will be conducted during club attendance approximately 3 months after the SKILLZ-Girl community soccer event; coaches will help them navigate the survey. If a participant has opted to not attend the clubs or has since left or changed schools, the coaches and study staff will attempt to trace participants in the community in order to complete the follow-up survey.

In the schools selected not to offer SKILLZ-Club, GRS will arrange for a 2-hour meeting session with all participants still enrolled at that school, where all participants will complete the surveys. If a participant opts to not attend the meeting or has since left or changed schools, the coaches and study staff will attempt to trace participants in the community in order to complete the follow-up survey.

The survey will record any changes to their home environment from baseline, again ask about self-reported sexual and risk behaviors and HIV knowledge (i.e., post-test for HIV education curriculum), and further quantitatively measure potential mediating pathways. Based on validated scales, the survey will include modules to assess stigma;⁵⁷ empowerment;⁵⁸ and self-efficacy⁵⁹ in general and specific to SRH/HIV;⁶⁰ disclosure, extent of social support from different sources (e.g., family, peers, teachers), and trust in health providers.⁶¹ Individual lost to follow-up (LTFU) will be traced following standard procedures. Active follow up and tracing of late or lost patients enrolled into HIV care or receiving ART is part of the National treatment program. We will partner with pre-existing CIDRZ community volunteers responsible for follow up to ensure that efforts are synchronized, and that data are shared and entered into SmartCare. CIDRZ already has an international reputation leading effort to track those who are lost to ensure participants return for visits and viral load testing as per national guidelines.⁹⁸

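### Follow-up surveys are run in different settings by arm, and longitudinal ascertainment is tied to SKILLZ-Club, which only enhanced schools have

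*Combined protocol and SAP*

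**What the plan says.** Section 8d (Data collection plan and tools) describes the follow-up survey separately for schools with and without SKILLZ-Club.

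- **Enhanced schools:** "surveys will be conducted during club attendance approximately 3 months after the SKILLZ-Girl community soccer event; coaches will help them navigate the survey".
- **SOC schools:** "GRS will arrange for a 2-hour meeting session with all participants still enrolled at that school, where all participants will complete the surveys". Nothing is said about who helps.
- **Fallback, worded identically for both:** for girls who do not attend or have left the school, "the coaches and study staff will attempt to trace participants in the community in order to complete the follow-up survey".

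Section 8c, discussing SKILLZ-Club, adds that "it is through the SKILLZ-Club affiliation that we will follow-up and ascertain outcomes for those enrolled longitudinally". The same section states: "Those schools randomized to standard SKILLZ Girl curriculum will only have access to SOC clubs".

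The surveys feed the effect estimates: "Post-SKILLZ-Girl survey data will be used to assess the effect of SKILLS Girl and SKILLZ-Club on the outcomes of interest" (section 8d). The baseline survey has a single description for all girls: "Coaches and study staff will on site be help girls navigate the survey". The primary analysis in section 8f regresses the outcome on arm interacted with a before/after indicator (POST), with GEE for clustering by school. It has no step for missing surveys or for ascertainment that differs by arm.

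**The concern.** In the enhanced arm, a session of the intervention is also a measurement session. SKILLZ-Club deals with HIV testing and contraception (section 4), and in that setting girls are asked about sexual behaviour, service uptake, empowerment and stigma. SOC girls answer in a meeting called for the survey.

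The first-line catchment differs as well. An SOC girl still in school is invited to the meeting. An enhanced-arm girl still in school who skips club has to be traced in the community. Both how girls report and who completes a survey could therefore differ by arm.

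Two features make this matter for the main comparison:

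- Take-home self-test kits are an enhanced-arm component (sections 4 and 7), and the documents describe no kit return or check of results. For tests done at home, the girl's own report may be the only evidence.
- The procedures are common at baseline and split afterwards. Difference-in-difference removes differences between arms that are constant over time. One that begins after allocation is counted as effect.

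**Working it through.** **Side-by-side reading**

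| Item | Enhanced | SOC | Explicit? |
|---|---|---|---|
| Baseline survey | One procedure; coaches and study staff help | Same | Yes |
| Survey at about 3 months: setting | Club session | Two-hour meeting, all still enrolled | Yes |
| Survey at about 3 months: helper | Coaches | Not stated | Enhanced arm only |
| 12 and 24 months | Through SKILLZ-Club, from section 8c | No SKILLZ-Club exists | Inferred |
| Tracing of non-attenders | Coaches and study staff | Same | Yes |

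**The plan's own power figure**

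Inputs from section 8c: 60% versus 80% tested, alpha 0.05 (sidedness not given; two-sided assumed), power 80%, ICC 0.1, about 100 girls per school, up to 18 schools.

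- Individually randomised requirement: 82 per arm.
- Design effect: 1 + (100 − 1) × 0.1 = 10.9.
- Effective size with 9 schools per arm: 900 / 10.9 = 82.6, giving power 80.7%. The stated 80% reproduces.
- With 8 per arm (16 schools, excluding the two pilots): 800 / 10.9 = 73.4, giving 75.8%.

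**Illustration 1: over-reporting in one arm.** Assume that 60% are truly tested in both arms, and that 10% or 20% of untested girls in one arm report a test.

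- Spurious difference: 0.40 × 0.10 = 0.04; 0.40 × 0.20 = 0.08.
- Null standard error, 8 schools per arm: √(2 × 0.60 × 0.40 / 73.4) = √(0.48 / 73.4) = 0.081.
- Shift in standard errors: 0.04 / 0.081 ≈ 0.49; 0.08 / 0.081 ≈ 0.99.
- Two-sided 5% t test, 14 df: rejection 7.5% and 15.2% instead of 5%.
- With 9 schools per arm (16 df): 7.8% and 16.7%.

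**Illustration 2: unequal loss, missing counted as untested.** Section 8c gives attrition as 12.5% in one place and about 15-20% in another. Neither is specific to an arm, and section 8f has no rule that missing means untested. Both are used here only as a scenario.

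- 0.60 × 0.875 = 0.525; 0.60 × 0.80 = 0.480; difference 4.5 points. The sign depends on which arm loses more.

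**Illustration 3: completers only.** Assume that 85% are surveyed in the enhanced arm and 75% in SOC, that 60% are truly tested in each, and that girls not reached were tested less often.

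- If 30% of unreached girls were tested: (0.60 − 0.15 × 0.30) / 0.85 = 0.653 versus (0.60 − 0.25 × 0.30) / 0.75 = 0.700, a difference of −4.7 points.
- If 45%: 0.626 versus 0.650, a difference of −2.4 points.

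Here better completion in the enhanced arm biases against the intervention. Swapping the completion rates reverses the sign.

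**The case against.** The strongest case on the other side is that the asymmetry is narrower than it looks and its size is unknown. Much of that stands.

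- **Tracing.** It is worded identically in both arms and will recover some girls missed at first contact. It does not equalise the setting, or who needs tracing.
- **Helper.** A reader might infer that coaches help only in the enhanced arm. The text is silent about the SOC meeting. Coaches help at baseline, deliver the curriculum in both arms and trace SOC non-attenders, so courtesy reporting to a coach is possible in both arms. The explicit difference is the setting.
- **Number of meetings.** A reader might infer that SOC girls are surveyed only once. The text does not say so; the meeting appears under a heading covering the post-event, 3-, 12- and 24-month surveys.
- **Later rounds.** Club administration is explicit only at about 3 months. Its extension to 12 and 24 months rests on the sentence in section 8c.
- **Data source.** It would go too far to say that the outcomes are all self-reported. Retention in HIV care and viral suppression come from SmartCare, and sections 8d and 8e also list the DREAMS and M.A.C. databases, laboratory data and programme data. The primary outcome includes tests at the event, before clubs begin. However, no source is named for the primary testing outcome, and nothing described would verify a home self-test.
- **Direction.** A reader might conclude that the bias favours the enhanced arm. The documents do not establish this: over-reporting would inflate the effect, while differential completion can push either way.

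**Conclusion.** The point holds as a design weakness that should be corrected. The survey setting differs by arm at about 3 months, the later rounds appear to differ as well, and the analysis plan has nothing to absorb the consequence. Because the split begins after a common baseline, any artefact sits in the estimated effect.

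Its size cannot be derived from the documents. Under the assumed rates above, it runs from about −5 to +8 points against a planned difference of 20, and over-reporting in one arm takes the type I error to about 7-15% with 8 schools per arm. These figures rest on assumed over-reporting and completion rates, 60% true testing in both arms, 100 girls per school and ICC 0.1. They show that plausible imbalances would matter, not that they will occur.

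**What to change.** 1. In section 8d, prescribe one follow-up procedure for both arms at 3, 12 and 24 months: the dedicated session already planned for SOC schools, outside club time, inviting all enrolled girls.
2. State the same helper roles for both arms. Where existing staffing allows, use study staff rather than the coaches who deliver the intervention. Keep the same tracing steps.
3. In section 8c, replace the sentence that runs ascertainment through SKILLZ-Club.
4. Report survey completion by arm and by mode (session or tracing).
5. If a sensitivity analysis restricted to documented tests is added, label it a conservative bound. It omits genuine home self-tests, mostly in the enhanced arm, so it brings in an arm-related misclassification of its own.

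The cost is about one extra two-hour session per enhanced school per round, plus some reallocation of staff time. That staff time should not be assumed free: study staff are named as helpers for the baseline survey, but at follow-up only for tracing.

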ongoing activity that students can participate in until they leave or graduate from school. Girls participating in the SOC Arm (SKILLZ-Girl) are able to join any of the other clubs currently offered at their school (SOC Clubs).

Clubs have been operating in schools in Zambia since 2017 with the MOGE's consent as part of the Memorandum of Understanding (MOU) signed in 2010 (*see Appendix B*). The CLUB component is currently evolving to include a more formalized education component, and will be piloted in Zambia at the same time as this evaluation.

4. All girls who test positive for HIV (whether prior to the SKILLZ-Girl event, during the event or as part of their participation in SKILLZ-Club) are referred to **SKILLZ-Plus**, a clinic-based initiative which provides HIV-infected girls access to ongoing support through a 12-week curriculum. During follow-up in the SOC Club arm, study staff will refer any newly identified HIV-positive girls to SKILLZ-Plus. In addition, study staff will refer newly diagnosed girls aged 16 years from neighboring clinics to the SKILLZ-Plus intervention.

For girls who test positive for HIV, either through a:

1. school referral either at the event, during club participation, are identified during follow-up or with a previously known diagnosis or
2. clinical referral (newly diagnosed only)

In addition, all girls found to be HIV-positive at any point throughout the SKILLZ-Program will be provided with intensive counselling support. Coaches will facilitate a family visit to facilitate disclosure and work with CIDRZ networks to provide additional psycho-social support as needed on a case-by-case basis by the participant.

SKILLZ-Plus provides several additional features:

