Within SKILLZ-Girl and SKILLZ-Club, our study will examine the additional benefits of offering access to two new health service offerings that are expressly designed to overcome barriers to uptake especially difficult for adolescents to overcome—HIV self-testing (HIVST) kits and access to an expanded method mix for contraceptive methods. Referral for contraceptive and SRH services will be made to the PEPFAR-funded DREAMS Houses or youth corners at local government facilities which are located within close distance to all schools where the SKILLZ package will be implemented.

Our mixed-methods evaluation will assess the effects of the enhanced SKILLZ offering (SKILLZ-Girl Enhanced & SKILLZ Club programs) compared to the SOC SKILLZ offering of SKILLZ-Girl only. Although the SKILLZ Program (Enhanced or SOC pending school allocation) will be offered to all girls enrolled in Grade 10 at selected study secondary schools, only girls aged 16 and over at the commencement of SKILLZ-Girl will be enrolled into the research study.

We will examine outcomes for school girls aged 16 and over enrolled in Grade 10 at the start of the intervention in up to 16 schools where the SOC SKILLZ Package is offered, compared to outcomes in up to 16 schools where the enhanced SKILLZ-Package is offered, including HIVST, the availability of expanded contraceptive services and the SKILLZ-Club following completion of SKILLZ-Girl. Therefore, all schools will be preassigned prior to the intervention into the following 2 categories (see **Figure 3** in *Section 8 - Methodology* below).

1. **SOC:** SKILLZ-Girl → Club SOC
2. **ENHANCED:** SKILLZ-Girl enhanced → SKILLZ-Club

Our central hypothesis is that the additional offering of HIVST and contraceptive services in an enhanced SKILLZ-Girl combined with the SKILLZ-Club offering will increase HIV testing and contraceptive uptake and continuation.

In addition to SKILLZ-Girl and SKILLZ-Club, girls testing HIV-positive at any time during the study intervention period will be additionally offered to participate in the SKILLZ-Plus facility-based curriculum for HIV-infected adolescents. The effect of the SKILLZ-Plus curriculum will be tested using a SmartCare-derived matched (i.e., on clinic, age, ART start date and gender) population.

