Economic evaluation: We will estimate the short- and long-term cost-effectiveness and return on investment of SKILLZ for improving health outcomes for adolescent girls.

Figure 2. Evaluation enrolment flow

b. Study site and population/Research materials

Lusaka is the capital and the most inhabited city in Zambia. Home to 2 million people, it has the highest HIV prevalence at 14%⁴. The study will take place across all the highly densely populated areas of Lusaka where

[figure not shown]
CIDRZ supports government MoH clinics with ARV services, electronic data management, and youth-friendly trained clinical personnel, and where GRS has been implementing their basic curriculum and events. All schools selected will be secular government schools. Approximately 80% of school-age girls are reported to be in school in Lusaka. To facilitate the evaluation of SKILLZ, all girls enrolled in up to 18 government secondary schools in Urban Lusaka that GRS currently serves will be eligible to participate in the SKILLZ program and will be randomly allocated to either the enhanced or SOC SKILLZ implementation. For measuring impact, only girls aged 16 and over enrolled in Grade 10 at the start of the intervention period will be surveyed and followed because youth aged 16 and over can consent for SRH/HIV services without additional parental permission⁵⁵. (See *Section 9: Ethical Considerations* for details on waiver of parental consent).

c. Selection of participants, sampling methods and sample size

Study Population: In each school, we will recruit all girls in Grade 10 who are at least 16 years old at the start of the intervention period (i.e., the commencement of SKILLZ-Girl). Of the 30,000 youth in Lusaka that have benefitted from GRS services to date, GRS has seen HIV testing uptake of 62% as compared to a baseline of 13% (internal program data). We have powered the sample for our primary endpoints in Aim 1ii to account for attrition anticipated along the cascade (see below). For HIV testing, all eligible girls (estimated to be an average of 100 girls per school) in up to 18 schools is large enough to detect a significant difference in testing uptake if setting statistical significance at $\alpha=0.05$, $\beta=0.2$, ICC=0.1, and an expected testing uptake of 60% (control) and 80% (intervention).

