Extraction of programmatic data: Quantitative measurements coming from programmatic data (e.g., frequency and attendance at SKILLZ-Plus meetings, frequency of home visits) will be collated from reports, supplemented with interviews of implementing staff (e.g., program managers and coordinators, coaches)

to track key process indicators. This may also be triangulated with programmatic-level information from the qualitative interviews.

e. Data management and storage

Quantitative:

We will collect individual-level data on clinical, laboratory, and demographic characteristics, including retention in care and VLS at 6, 12 and 24 months. Using case reporting forms (CRFs), we will collect study-specific data, including information obtained directly from participants, routine programmatic data from GRS and abstract routine clinical data from paper-based medical records, the SmartCare Electronic Management Records (EMR), CIDRZ Laboratory Information Management System (LIMS) and DREAMS electronic management system. Routinely collected individual-level clinical data are first written onto forms in the paper medical record and then entered into the SmartCare EMR. SmartCare serves as a repository of clinical data for HIV-infected individuals and includes such data fields as: ART initiation date, ART regimen, visit dates, and laboratory data.

GRS will collect programmatic data through a combination of paper and electronic data entry via tablets, with all data stored securely in RedCap. Where paper files are used for programmatic management, data will be manually entered by study staff directly into the RedCap database. De-identified data will be made available to GRS co-investigators to allow them to view key fidelity and quality indicators in order to monitor implementation in real time.

All paper study files will be stored in secured, locked cabinets located in locked rooms available to study staff only. The keys to the locked cabinet will be kept by study staff and not made accessible to non-study personnel.

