Difference-in-difference model. The primary outcome is the probability of testing for HIV at any time during the period when SKILLZ is delivered through to 24 months after the final soccer event. The primary analysis for Aim 1 will follow a difference-in-difference (DID) effect between study arms. The outcome of interest will be regressed on an indicator of study arm assignment interacted with a dichotomous variable POST which indicates the outcome after the intervention is implemented; this differentiates baseline and end-line for each study arm, controls for any time dependent variables that might confound the effect, as well as any time-invariant observed or unobserved confounders that might differ between study arm schools. Because of this, the DID is robust to time-invariant unobservable confounders (e.g., school quality) and time trends (e.g., secular increase in testing). Our estimator relies on the assumption of common time trends across intervention and control in absence of the intervention, and of static population. Additionally, we control for baseline individual and school-level moderators that may be unbalanced at baseline after randomization. School-level controls include size, promotion rates, sex composition and repetition and dropout rates (available in the district education office) and individual girls' controls include age, grade, maternal education, HIV knowledge. Clustering by school will be accounted for by a generalized estimating equation approach. We will estimate intention-to-treat (ITT) by including all girls in the evaluation cohort assigned to each arm rather than all girls who actually participated in SKILLZ.

Individual-level matched cohort analysis for HIV-infected: The analysis will follow an individual ITT estimator among individuals found to be HIV-infected, who will then be matched (based on clinic, age, ART state date, and gender) to HIV-infected individuals in the SmartCare database. The outcomes are the proportion of enrolled HIV+ girls who linked to care, who are virally suppressed and retained in care at 6, 12, and 24 months after diagnosis of HIV+ (using national electronic HIV medical record data). We will conduct an ITT analysis for the logistic probability of being suppressed at 6, 12, and 24 months after HIV+ diagnosis, where girl is the unit of analysis. All data will be analyzed using STATA.

Process evaluation: This will involve quantitative and qualitative analyses:

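### The SmartCare comparison for SKILLZ-Plus takes no account of viral suppression or attendance at entry, so any imbalance the four-variable match leaves passes into the estimated effect, in an unknown direction

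*Combined protocol and SAP*

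**What the plan says.** The matching set appears twice, with the same four variables. Section 4 describes a SmartCare-derived "matched (i.e., on clinic, age, ART start date and gender) population". Section 8f (individual-level matched cohort analysis) has HIV-infected girls "matched (based on clinic, age, ART state date, and gender) to HIV-infected individuals in the SmartCare database"; the wording there is plainly a slip for ART start date. Section 7, Aim 1(ii), adds only that the groups come from the same district and that the SmartCare records are of people in care.

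The outcomes are statuses at 6, 12 and 24 months, not changes from entry. Section 8d states "VLS is defined as below detection, i.e. less than 50 copies/ml" and defines retention from pharmacy visits. Section 8f fits a logistic model for being suppressed. It names no covariate for entry viral load, regimen or earlier attendance, and excludes nobody who was suppressed at the start.

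Section 4 lists the routes into SKILLZ-Plus. School referrals include girls who "are identified during follow-up or with a previously known diagnosis". Only the other route is restricted: "clinical referral (newly diagnosed only".

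The missing variables are of a kind SmartCare records. Section 8d says of SmartCare "which permits measuring of utilization and clinical outcomes (i.e., Linkage to Care, VLS", and section 8e says it "includes such data fields as: ART initiation date, ART regimen, visit dates, and laboratory data".

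**The concern.** This comparison is not randomised, so it depends on the groups being alike at the start. For a girl already on ART, whether she is suppressed and collecting her drugs at entry is likely to be a strong predictor of the same status a year later. The match contains neither. Matching on ART start date balances time since treatment began, but not what has happened since. Section 5 cites programme data in which close to half of adolescents who know their HIV status are lost to care inside two years of starting ART, so girls with the same start date can be in very different positions.

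The plan does adjust the school comparison for baseline factors that may be unbalanced after randomisation. The SmartCare comparison, where imbalance is more likely, has no such step. At stake is whether a positive, null or negative SKILLZ-Plus result on suppression and retention can be interpreted at all for previously diagnosed girls.

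**Working it through.** The plan gives no figure to reproduce. Section 8c says the sample was powered for Aim 1(ii) endpoints, but states no rates, effect size or number for the matched comparison. The check is therefore a reading of the text followed by an illustration.

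**Reading the sections together**

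1. Section 4 admits girls with a known diagnosis, so some may be on ART and suppressed at entry.
2. Sections 4 and 8f do not match on entry viral load, regimen or attendance, and 8f does not adjust for them.
3. Section 8f counts suppressed status at follow-up, so entry status carries through in both groups.
4. Section 8c starts the clock at diagnosis or, alternatively, when the programme identifies the girl as positive; section 8f starts it at diagnosis. Under 8f, a girl diagnosed years earlier could have all three time points fall before SKILLZ-Plus. No section gives comparators an index date.

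**Size of the carry-over, with no programme effect**

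Let s be the share suppressed at entry, a the chance that a suppressed girl is suppressed at follow-up, and b the same chance for a girl not suppressed at entry. If a and b are equal in both groups:

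- follow-up suppression = s × a + (1 − s) × b
- spurious difference = (s₁ − s₀) × (a − b), where 1 is SKILLZ-Plus and 0 is comparators.

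Inputs: a = 0.85 and b = 0.30 are assumed. The 34% is the figure section 1a gives for suppression in adolescent girls, used as one possible comparator value. The 45% and 60% are assumed.

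- s = 0.34: 0.34 × 0.85 + 0.66 × 0.30 = 0.487
- s = 0.45: 0.45 × 0.85 + 0.55 × 0.30 = 0.5475
- s = 0.60: 0.60 × 0.85 + 0.40 × 0.30 = 0.630

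| SKILLZ-Plus at entry | Comparators at entry | Spurious difference |
|---|---|---|
| 45% | 34% | 0.5475 − 0.487 = about +6 points |
| 60% | 34% | 0.630 − 0.487 = about +14 points |
| 45% | 60% | 0.5475 − 0.630 = about −8 points |

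**Range.** With a from 0.85 to 0.95 and b from 0.3 to 0.7, a − b runs from 0.15 to 0.65. A 10 to 30 point imbalance then gives 10 × 0.15 = 1.5 up to 30 × 0.65 = 19.5 points, with the sign of the imbalance.

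**After correction.** If entry suppression is balanced, s₁ − s₀ = 0 and the spurious difference from this source is zero for any a and b. Comparing girls within the same entry status does the same.

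**Group size.** Section 8a expects about 98% of girls tested to be negative, so about 2% positive. If every girl were tested, 1,800 girls (18 schools × 100, section 8c) give 1,800 × 0.02 = 36, and the starting sample of 3,159 gives 3,159 × 0.02 = about 63. The number already on ART is not stated.

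**The case against.** A reader might infer that girls already suppressed at entry are credited to SKILLZ-Plus. The documents do not support that as a one-sided error: comparators who were already suppressed count as successes too, and matching on clinic and ART start date balances part of the treatment history. Bias arises only if entry suppression or attendance still differs after matching, and nothing in the documents shows that it does.

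A reader might also infer that the bias favours SKILLZ-Plus, because schoolgirls who come forward may be better engaged. Section 8b notes "Approximately 80% of school-age girls are reported to be in school in Lusaka", and comparators may include girls outside school. But Aim 1(ii) draws comparators from people already in care, who could be the better-suppressed group. The 34% in section 1a does not describe girls on ART, and section 3a cites a youth cohort in another country with 77% suppressed. The sign is open.

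Three further limits stand. The problem concerns previously diagnosed girls on ART; newly diagnosed, untreated girls would mostly be unsuppressed at entry. Aim 1(ii) can be read as covering only girls identified during the programme, but section 4 names known diagnoses and section 8c provides a start date suited to them. And section 8e shows that SmartCare has laboratory fields, not that every girl has a viral load before entry.

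**Conclusion.** The gap is real, and the plan should close it. As written, any difference between groups in entry suppression or earlier attendance becomes part of the estimated SKILLZ-Plus effect among previously diagnosed girls. On the stated assumptions it could be about +6 or +14 points, or about −8, with no programme effect. These figures illustrate the mechanism: a, b and the imbalance are assumed and apply to girls already on ART, so the bias in the whole group shrinks as the share of newly diagnosed girls grows. Neither the presence of an imbalance nor its direction can be established from the documents. The unknown sign is itself a reason to adjust, since without adjustment neither a positive nor a null finding could be read with confidence. The HIV-testing outcome that section 8f names as primary is unaffected.

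**What to change.** In section 8f, for Aim 1(ii):

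1. Define one index date for both groups, reconciling section 8c (diagnosis, or identification by the programme) with section 8f (diagnosis). Give each comparator of a previously diagnosed girl an equivalent date at the same time since ART start. State the rule separately for newly diagnosed girls, who may have no ART start date at that point.
2. Adjust for SmartCare values before the index date, with the same look-back in both groups: last viral load (suppressed, not suppressed, none recorded), ART regimen, and recent pharmacy-visit attendance. Adjustment is more workable than exact matching on three more variables in so small a group.
3. Report newly diagnosed and previously diagnosed girls separately.
4. Describe the result as an association, because schooling and route to diagnosis are not among the SmartCare fields listed.

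Several comparators per girl would help precision but are optional. The cost is plan wording and extra fields in an extract already planned. Some viral loads before the index date will be missing, and the subgroups will be small and imprecise.
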